8.4	Disclosure and confidentiality.....	27
8.5	Data protection.....	27
9	Reporting of results.....	28
9.1	Study report	28
9.2	Progress report and interim report of study results (PASS)	28
9.3	Publication of results	28
10	Reference list.....	30

Table of figures

Figure 1	Study design.....	12
----------	-------------------	----

Table of tables

Table 1	Amendments and updates of the protocol	7
Table 2	Flow chart	9
Table 3	Study milestones.....	13

List of abbreviations

AIT	Allergy immunotherapy
AE	Adverse event
ART	Antibody responder test
Bet	Betula verrucosa
CCSI	Company core safety information
CRF	Case report form
eCRF	Electronic case report form
FeNO	Fractionated exhaled nitrogen oxide
HDM	House dust mite
IEC	Independent ethics committee
IRB	Independent review board
MAH	Marketing authorization holder
MedDRA	Medical dictionary for regulatory activities
NIS	Non-interventional study
PASS	Post-authorisation safety study
PFS	Pollen food syndrome
SAE	Serious adverse event
SCIT	Subcutaneous allergy immunotherapy
SmPC	Summary of product characteristics
SOP	Standard operating procedure
SLIT	Sublingual allergy Immunotherapy
SLIT-drops	Sublingual allergy immunotherapy drops
SLIT-tablets	Sublingual allergy immunotherapy tablets
SQ	Standardised Quality
TRAE	Treatment-related adverse event
WHO	World Health Organisation

Protocol synopsis

Title:	ITULAZAX Post Authorization Safety (IPAS) Study: A prospective, non-interventional study assessing the safety and tolerability of ITULAZAX in adults with tree pollen allergy in real-life practice
Study ID:	NI-TT-01
Development phase:	IV, non-interventional post-authorization safety study (PASS)
Rationale and background:	In the clinical development programme the ITULAZAX was observed to be well-tolerated. However, no safety and tolerability data for the product from the use in a routine care setting are available. This non-interventional observational PASS is conducted in order to document the safety and tolerability of the ITULAZAX in real-life clinical practice.
Primary objective:	To investigate the safety and tolerability of the ITULAZAX in adults (18-65 years of age) in the first 4-6 months of treatment in a real-life setting.
Study design:	Non-interventional, observational, multi-site, open-label multi-national PASS to investigate the safety and tolerability of ITULAZAX in adult patients in a real-life setting in Germany, the Netherlands, Denmark, Sweden, Norway and Finland.
Study population:	
The selection of patients is at the discretion of the investigator, enrolment can be offered to patients:
 
- Who are prescribed ITULAZAX according to the current version of the approved national SmPC 
In addition, enrolment requires that a written informed consent by the patient is obtained before initiation of any study-related activities.

Study size:	A total of approximately 1000 adult patients are planned to be included in the study. A planned number of 50 investigators in Germany, 80 in the Netherlands, 10-12 in Denmark, 10-12 in Sweden, 10-12 in Norway, 10-12 in Finland are expected to participate.
Assessments:	At baseline: demographics, body measurements, previous and concomitant medication, medical history, concomitant diseases and medication baseline allergy symptoms, immunoglobulins (IgE, IgG4) and fractionated exhaled nitrogen oxide (FeNO), if routinely measured, first intake of SQ tree SLIT-tablet. All assessments shall only be performed if they are done routinely

Template
TPL48761
Signature: OnPaper

NI Protocol

by the treating physician.

At follow-up visits, since last visit: adverse events (AEs), allergy symptoms, symptoms of pollen food syndrome (PFS), symptomatic medication, antibody responder test (ART), if routinely performed in investigator's practise, FeNO, if done; first administration of other SLIT-tablets, if applicable.

Data sources: Data will be entered by the physician in an electronic case report form (eCRF).

Statistical methods: AEs as well as breakdown of AEs and treatment-related AEs (possibly related) according to seriousness, severity and causality will be summarised for AEs during administration (V1 to V4).

AEs will be summarised by MedDRA System Organ Classes and MedDRA Preferred Terms displaying number of patients, frequency of patients having AEs as well as number of AEs.

Missing data will not be replaced.

Product: ITULAZAX

Country(ies): Germany, Netherlands, Denmark, Sweden, Norway, Finland

Study milestones:	Planned first patient first visit:	Mar 2020
	Planned last patient last visit:	Jun 2022
	Planned final study report:	Jun 2023

Amendments and updates

Amendments and updates of the protocol are summarised in Table 11.

Table 1 Amendments and updates of the protocol

Number	Date	Version	Description of document
1	10 Sep 2019	1.0	Final Protocol
2	13 Jan 2020	2.0	
Table 2, Flow chart: Time frame V2, V3, V4 changed from 4-12 weeks to 1-3 months to be consistent with text above.
 
Study milestones) updated (Section 3.3 and Synopsis):
 
 - Planned last patient last visit changed from Oct 2021 to Jun 2022 - Planned final study report changed from Oct 2022 to Jun 2023. 
Section 2.1: Treatment period corrected from 4 to 4-6 months aligned with Section 3.1 and Synopsis.

3	29 Apr 2020	3.0	
 - Study milestones, Planned first patient first visit updated to “Mar 2020” (Section 3.3 and Synopsis). - List of abbreviations: “MAH, Marketing authorization holder” added. - Section 3.2.2 Secondary endpoints: bullet 5 and 6, observation period adjusted to: “... the first 4-6 months of treatment”. - Section 4.2 Collection, recording and reporting of adverse events: 
 - Local safety contact persons/Germany: “[name]” deleted and replaced by: “[name] and [name]. [name]” - Reference Safety information (RSI) document, changed to: “Assessment of expectedness of non-serious AEs and SAEs for submission purposes will be performed by the MAH according to the reference safety information which is the current approved Company Core Safety Information (CCSI). In case the CCSI is changed during the study, the expectedness assessment will be done acc. to the updated CCSI by the MAH. - Pregnancy: 2nd paragraph, 2nd sentence “observed by the investigator or reported by the subject must be recorded and evaluated via the AE form and reported to ALK within 14 days of obtaining knowledge

Template
TPL48761
Signature: OnPaper

NI Protocol

			of the event via the AE form provided in the eCRF." Deleted.
	28 May 2020	3.0	Section 4.2 Collection, recording and reporting of adverse events, paragraph "Reference Safety Information (RSI) document" deleted.
4	04 October 2022	4.0	Title page (page 1): Address of sponsor (street name) changed from: "[name]" to "[name]".

Flow chart

A total number of maximum 4 visits was planned during the study; visit 1 (baseline), visit 2 (1-3 months after visit 1), visit 3 (1-3 months after visit 2) and visit 4 (final visit, 1-3 months after visit 3). Please refer to the flow chart in Table 2 for a summary and timing of planned visits, and the procedures planned at each visit.

Table 2 Flow chart

Visit ID	V1	V2	V3	V4
Time frame	Day 0	1-3 months after V1	1-3 months after V2	1-3 months after V3
Visit window	± 10 days	± 10 days	± 10 days	± 10 days
Informed consent	X			
Demography and body measurements	X			
Patient eligibility	X			
History of allergy (incl. PFS)	X			
Diagnostics, as far as available	X			
Previous (completed) immunotherapy(ies)	X			
Concomitant immunotherapy(ies)	X	X	X	X
Relevant previous and concomitant medication	X	X	X	X
Previous and concomitant illness	X	X	X	X
Allergy symptoms	X	X	X	X
PFS-symptoms	X	X	X	X
Symptomatic medication	X	X	X	X
Antibody Responder Test (ART), if performed		(X)	(X)	(X)
Handout of patient videos about AIT/side effects	(X)	(X)	(X)	(X)
Fractionated exhaled Nitric oxide (FeNO), if	(X)	(X)	(X)	(X)

performed				
First administration of ITULAZAX	X			
Assessment of AEs	X	X	X	X
Global assessment of tolerability at final visit			(X)	X
Study completion/withdrawal	(X)	(X)	(X)	X

1 Introduction

ITULAZAX achieved marketing authorization for sublingual allergy immunotherapy in adult patients with allergic rhinitis due to allergens from the birch homologous group in July 2019 in Denmark, Germany, Norway and Sweden, and in August 2019 in Finland and in the Netherlands after a clinical development program comprising clinical trials in phase 1 to 3. The current non-interventional PASS is conducted to record first data on safety and tolerability of ITULAZAX during routine treatment in real-life.

In the clinical development program ITULAZAX was observed to be well-tolerated. Most frequently reported adverse events were mild-to-moderate local allergic reactions related to the sublingual administration. As ITULAZAX is intended for treatment of an allergic disease by exposing the subject to the allergen, there is a risk that the treatment can trigger systemic allergic reactions. In rare cases, a systemic allergic reaction can develop into an anaphylactic reaction or shock. The risk of anaphylactic reactions is low and is mitigated through labelling with relevant precautions and guidance for treatment. To prevent the use of ITULAZAX in patients who are at increased risk of severe systemic allergic reactions, a number of risk minimisation measures have been introduced in the product information. While the most common adverse events experienced as pruritus and discomfort are inconvenient for the patient but do not impair the safety of the treatment, adverse events with severe swelling and/or systemic reactions observed in some patients treated with SLIT-tablets need the physician's particular attention. Therefore, in this non-interventional observational PASS, the safety and tolerability of ITULAZAX will be evaluated in real life settings in allergological practice. The study will gain initial experience with the treatment of adult patients with ITULAZAX under routine conditions of everyday practice.

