3.5.2 Patient discontinuation

The patients will be advised that he/she have the right to discontinue from the study at any time without prejudice.

Furthermore, the patient may also be discontinued from the study at the discretion of the investigator, e.g. in case of AEs or treatment discontinuation.

In case of discontinuation, the investigator should attempt to collect any outstanding data, if possible. The investigator should inquire about the reason for discontinuation (adverse event, non-compliance with protocol or other) and specify this in the case report form (refer to Section 4).

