3.7.4 Visit 4 (final visit)

The following procedures should be performed at visit 4:

- Assessment of AEs since last visit (incl. FU-information on previous AEs)
- Pregnancy (yes, no)
- Changes in relevant concomitant diseases and medical treatments
- Adherence estimate (average frequency of tablet intake, reasons for not taking the tablet)
- Allergy symptoms since last visit (nose, eyes, bronchial, skin)
- PFS-symptoms since last visit
- Symptomatic medication since last visit
- If applicable and done in routinely use: Fractional exhaled nitric oxide (FeNO) (result (ppb FeNO), if performed).
- If applicable and done in routinely use: Patient video
- First administration of other SLIT-tablet (date/time of application, anti-allergic premedication, AEs), if applicable
- If applicable and done in routinely use: Antibody Responder Test (ART), (ART generally applied, if yes results IgE, IgG4, neg./pos., ART score)
- Global assessment on tolerability by physician and patient

Template
TPL48761
Signature: OnPaper

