3.8.6 Follow-up (visits 2-4)

History since last visit (AEs since last visit, follow-up information on previously documented AE since last visit, pregnancy, change in medical treatment(s) of concomitant disease(s) since last visit

Allergy symptoms since last visit (none/mild/moderate/severe) nose symptoms, eye symptoms, bronchial symptoms, skin symptoms

Symptoms of the PFS since last visit, if applicable

Symptomatic medication since last visit

ART, FeNO measurements, if routinely performed

First administration of other-SLIT-tablets: date/time of first administration, pre-medication given (no/yes, if yes preparation time (minutes, seconds before SQ tree SLIT-tablet intake), AEs after first administration of SQ tree SLIT-tablet, if applicable

Global assessment of tolerability by physician and patient (very good/good/moderate/poor).

4 Adverse events

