7.4 Safety analysis

AEs as well as breakdown of AEs and treatment-related AEs (possibly related) according to seriousness, severity and causality will be summarised for AEs during administration (V1 to V4).

AEs will be summarised by MedDRA System Organ Classes and MedDRA Preferred Terms displaying number of patients, frequency of patients having AEs as well as number of AEs.

Missing data will not be replaced.

8 Protection of human subjects

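### The global tolerability rating has no clear slot for patients who withdraw before V3, so this supportive item risks favourable selection

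*Protocol*

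**What the plan says.** The rating appears in three places in the protocol, and they do not match.

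- **Table 2 (flow chart).** The row "Global assessment of tolerability at final visit" is blank at V1 and V2, (X) at V3 and X at V4. The row "Study completion/withdrawal" is (X) at V1, V2 and V3 and X at V4.
- **Sections 3.7.1 to 3.7.4 (visit procedures).** The rating, worded "Global assessment on tolerability by physician and patient", is listed only for V4. The V3 list omits it, although section 3.1 plans three or four visits and section 3.7.3 schedules V4 only if applicable.
- **Section 3.8.6 (follow-up, visits 2-4).** It lists "Global assessment of tolerability by physician and patient (very good/good/moderate/poor" with no restriction to a particular visit.

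Section 3.5.2 allows the investigator to take a patient out of the study, "e.g. in case of AEs or treatment discontinuation". It adds: "In case of discontinuation, the investigator should attempt to collect any outstanding data, if possible". It also asks for the reason: "The investigator should inquire about the reason for discontinuation (adverse event, non-compliance with protocol or other". The global rating is not named there. Section 7.4 states: "Missing data will not be replaced".

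**The concern.** Whether a rating is missing would depend on the thing being rated. Patients who stop before V3 because of adverse events probably tolerated the tablet worse than those who stayed. If sites follow the flow chart or the visit lists as written, those patients are not rated, and the summary describes mainly people who tolerated treatment well enough to continue.

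The exposed period is long. V2 falls 1-3 months after V1 and V3 a further 1-3 months later, so V3 comes 2-6 months after V1, before the visit windows are applied. Section 3.1 plans follow-up of 4-6 months, 4 on average. Much of a patient's follow-up, and in some cases all of it, can pass before the first scheduled rating.

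Tolerability is part of the primary objective (section 2.1), and this rating is the only overall judgement of it by physician and patient. An analysis plan cannot recover a rating that was never taken.

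**Working it through.** **1. The schedule, side by side**

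| Item | V1 | V2 | V3 | V4 |
|---|---|---|---|---|
| Completion/withdrawal (Table 2) | (X) | (X) | (X) | X |
| Global rating (Table 2) | – | – | (X) | X |
| Global rating (3.7.1-3.7.4) | – | – | – | listed |
| Global rating (3.8.6) | – | visits 2-4, not restricted | same | same |

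If the flow chart meant each patient's own last visit, the rating row would be expected to carry (X) wherever the withdrawal row does. It does not at V1 and V2. Taken alone, section 3.7.3 would also leave patients who finish at V3 unrated. Table 2 allows a rating there, so that part is a mismatch to align.

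**2. The only related rate in the document**

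Section 1.1 reports that 25 subjects (8%) in the active group of TT-04 discontinued because of AEs. With 634 subjects randomised 1:1, the active group is about 634/2 = 317, and 25/317 = 7.9%, which agrees with the printed 8%. The protocol has no sample size calculation or precision statement that this point could be checked against.

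**3. Illustration of size**

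Inputs:
- d = share discontinuing for AEs = 8% (TT-04), about 80 of the planned 1000
- m = the part of d left unrated: all, half or none (assumption)
- pC = share rating 'poor' among stayers = 5% (assumption)
- pW = share who would rate 'poor' among AE withdrawers = 50% or 100% (assumption)

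Formulas:
- Observed 'poor' = [(1 − d)·pC + (d − m)·pW] / (1 − m)
- Full-cohort 'poor' = (1 − d)·pC + d·pW

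Results, with (1 − d)·pC = 0.92 × 0.05 = 0.046:

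| Unrated | pW | Observed | Full cohort | Gap (points) |
|---|---|---|---|---|
| All (m = 0.08) | 100% | 0.046/0.92 = 5.0% | 0.046 + 0.080 = 12.6% | 7.6 |
| All (m = 0.08) | 50% | 5.0% | 0.046 + 0.040 = 8.6% | 3.6 |
| Half (m = 0.04) | 100% | 0.086/0.96 = 9.0% | 12.6% | 3.6 |
| Half (m = 0.04) | 50% | 0.066/0.96 = 6.9% | 8.6% | 1.7 |
| None (m = 0) | either | equals full cohort | 12.6% or 8.6% | 0 |

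With d from 4% to 12%, pC from 5% to 10%, pW from 50% to 100%, and half or all unrated, the gap runs from 0.8 to 11.4 points. The direction is favourable whenever withdrawers would rate worse than stayers.

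**The case against.** A reader might infer that early withdrawers never rate tolerability and that the study's tolerability result as a whole is therefore biased. The documents do not support either inference.

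- **Never rated.** Section 3.8.6 places the rating under visits 2-4, section 3.5.2 asks for outstanding data where possible, and the final visit in the flow chart row could be read as the patient's own last visit. The text is ambiguous; it does not exclude a rating. The ambiguity is still a defect, because a rating not scheduled before V3 is not clearly outstanding at V1 or V2.
- **The whole tolerability result.** The rating is neither a primary nor a secondary endpoint (section 3.2), and section 3.4 says the AE-based endpoints and adherence are suited to addressing safety and tolerability. AEs are collected from consent (section 4.2) and assessed at every visit. The Safety Set holds everyone with at least one administration (section 7.2), and the reason for discontinuation is recorded. Intolerance that leads to withdrawal is therefore still visible there. This stands, and it confines the point to one supportive item.
- **Size.** It is also tempting to read 12.6% against 5.0% as an estimate. It is the worst of the cases at 8%: every AE withdrawal unrated, and every one of them 'poor' on a four-level scale. Section 1.1 describes the events behind the TT-04 discontinuations as mainly mild or moderate. The 8% also covers that whole trial, in subjects aged 12-65, and the protocol does not say how many patients would stop before V3 here.
- **Reporting.** Denominators and table layout can be left to an analysis plan. The no-replacement rule does not prevent the unrated from being counted.

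**Conclusion.** The point holds for the global rating only. Three parts of the protocol disagree on when the rating is made, and none clearly schedules it for a patient who withdraws at V1 or V2, although withdrawal for AEs is foreseen. Followed as written in the flow chart or the visit lists, the schedule selects the rating towards patients who tolerated treatment.

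This is a risk of favourable selection, not a demonstrated bias, and its size is not fixed by the documents. At the TT-04 discontinuation rate of 8%, with 5% 'poor' among stayers and 50-100% 'poor' among withdrawers, the understatement is about 1.7 to 7.6 points if half to all withdrawers go unrated. It is zero if all are rated. Only the 8% comes from the protocol; the other inputs are assumptions. The correction is worth making because it is nearly free and the missing ratings cannot be recovered later.

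**What to change.** - Reconcile Table 2, sections 3.7.2 to 3.7.4 and section 3.8.6 by requiring the rating at each patient's last visit, including V3 when it is final and any withdrawal contact.
- In Table 2, mark the rating (X) at V1 and V2 for patients who withdraw there. Add it to section 3.7.3 for patients finishing at V3, and to the withdrawal page of the eCRF. Name it in section 3.5.2 among the data to collect at discontinuation.
- Report the number of patients not rated, by reason for discontinuation. The layout can be left to the analysis plan.

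Unrated withdrawals should not be recoded as 'poor'. That would impute a value the patient never gave, against the no-replacement rule in section 7.4.

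The cost is a change to one flow-chart row, a small eCRF change to an existing item, and probably a slightly less favourable rating. Version 4.0 is dated October 2022, after the planned last patient visit in June 2022. If collection has in fact ended, only the reporting step remains, and the report should say that the rating comes mainly from patients still in the study at V3 or V4, if the data show this.

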1.1 Background

The clinical development program for ITULAZAX comprised 4 clinical trials in Phase 1 to 3.

Trial TT-01 was a randomized, multiple dose, dose escalation, double-blind, placebo-controlled trial in phase 1 investigating the safety of ITULAZAX in adult subjects with birch pollen-induced rhinoconjunctivitis (with or without asthma) conducted in Denmark including 70 subjects [1].

Trial TT-02 was a randomized, parallel-group, double-blind, placebo-controlled, multinational trial in phase 2 conducted in Europe (DK, FIN, LT, NL, NO, PL, SE) to investigate the dose-related efficacy and safety including 637 subjects [2].

Template
TPL48761
Signature: OnPaper

Trial TT-03 was a randomized, double-blind trial conducted to determine the optimal dose for clinical efficacy of ITULAZAX in an environmental exposure chamber (EEC) including 219 subjects [3].

TT-04 was the pivotal trial in phase 3 to demonstrate efficacy and safety of ITULAZAX including 634 subjects [4].

In trial TT-01 doses up to 12 SQ-Bet were considered suitable for home-treatment, trial TT-02 showed a dose-response effect for doses of 2 to 12 SQ-Bet and trial TT-03 identified 12 SQ-Bet as optimal dose.

Trial TT-04 was a randomized, double-blind, placebo-controlled trial with 634 randomised subjects (aged 12-65 years) with moderate-to-severe allergic rhinoconjunctivitis despite use of symptom-relieving medication. Subjects were randomized 1:1 to active or placebo treatment. The primary endpoint was the average daily allergic rhinoconjunctivitis total combined score (TCS) during the BPS analysed for subjects with diary data during the BPS. Secondary endpoints included average daily symptom score (DSS) during the birch pollen season (BPS), average TCS and DSS during the entire tree pollen season (TPS) and average daily medication score (DMS) in the BPS and TPS. The primary and secondary endpoints demonstrated statistically significant and clinically relevant effects of ITULAZAX compared with placebo. Relative differences for the BPS from placebo were 40% for the TCS, 37% for DSS and 49% for DMS (all $p < 0.0001$). For the TPS relative differences were 37% for the TCS, 33% for DSS and 47% for the DMS (all $p < 0.0001$).

The trial demonstrated the efficacy and safety of ITULAZAX versus placebo during the BPS and TPS in adolescents and adults with birch pollen-induced allergic rhinoconjunctivitis.

In general, treatment was well tolerated. The most frequently reported treatment-related adverse events (TRAEs) were mild-to-moderate local reactions related to sublingual administration of the tablet, the most common events were oral pruritus and throat irritation. Twenty-five (8%) subjects in ITULAZAX group discontinued the trial because of 98 AEs. These were mainly characterised as irritation or swelling in the mouth or throat of mild or moderate intensity.

The safety and tolerability during routine treatment in real life will be investigated in this Non-interventional-PASS.

The safety and tolerability profile and expected frequencies according to the clinical trials with ITULAZAX are described in the Summary of Product Characteristics (SmPC), [5].

